9.1.1. Screening Phase and the Pre-CPB Phase

The Screening Phase through the Pre-CPB Phase is the period bound by the time that consent is provided for study participation and the start time of CPB. Subjects are qualified for study participation by confirmation of meeting all the inclusion and none of the exclusion criteria.

Each enrolled subject will be assigned a unique Subject Number consisting of a Site Number assigned by the Sponsor or designee, and a number which is sequentially assigned to all subjects screened at the investigation sites (e.g., XXX-YYY, where XXX is the site number and YYY is the subject number). The Subject Number will be used as a subject identification for each subject throughout the investigation.

Screening and pre-CPB assessments should be completed as detailed in [Table 6](#). As discussed in [Section 1.1](#), all subjects undergoing CABG or with recent coronary stent placement (within prior 6 months) should have aspirin continued going into surgery. An overview of antithrombotic and anticoagulation management for study subjects is provided in [Appendix 4, Table 5](#). During Screening, if consented subjects enter the Operation Phase without *post-consent* clinical chemistry, cardiac troponin, hematology, or coagulation tests to record, the last pre-consent laboratory values MAY be used.

Pre-randomization stratification

Pre-randomization stratification will be performed on three levels (see [Section 6.1](#) for details):

1. By DOAC type (either apixaban or rivaroxaban);
2. By study site;
3. By the planned surgical procedure:
 - Isolated CABG (irrespective of number of grafts); or
 - All other cardiothoracic procedures requiring CPB.

Randomization

Subjects will be prospectively randomized in a one to one (1:1) fashion to either the control arm (SOC) or to the investigation arm (SOC + DrugSorb-ATR), as detailed in [Section 6.2](#).

9.1.2. Operation Phase

The Operation Phase will be initiated at the time of first incision. During the Operation Phase, the subject will either undergo standard CPB, or CPB + DrugSorb-ATR according to randomization.

Subjects randomized to the control arm will receive standard of care in which a sham device will be in place parallel to the CPB circuit, but through which no blood will circulate. Refer to [Section 6.3](#) for details.

In the treatment arm, DrugSorb-ATR treatment will initiate with the start of CPB and continue through the end of CPB. Per the IFU and under the guidance of a Field Clinical Specialist, the DrugSorb-ATR cartridge will be placed into a parallel bypass circuit to the main blood flow in a standard CPB circuit and primed for use in preparation for the Operation Phase. Throughout the treatment session, the DrugSorb-ATR setup will be monitored for blood leaks, flow changes, and/or clots. Any adverse device events and/or device observations must be recorded by indicating the location of leaks and/or by recording the size of any clots present. DrugSorb-ATR treatment flow rates will be controlled utilizing a roller clamp placed on the distal, superior line above the DrugSorb-ATR prior to returning to the reservoir. Flow rate will be measured using a Sponsor provided Transonic® (or equivalent) ultrasonic flow meter and probe, placed on the inlet line below the DrugSorb-ATR device. **The blood flow rate through the device will be adjusted to 500mL/min ± 100mL/min.**

During the operation phase, arterial blood gas analysis will be obtained at the following time periods: within 30min pre-CPB, 30 ± 15 min into CPB, within 30 minutes post-CPB, and upon admission to the ICU. Activated clotting time will be obtained once at 30 ± 15 minutes into CPB, and once *within 30 minutes* post-protamine administration. All other assessments including monitoring of transfusions, will be performed as detailed in [Table 6 of Appendix 4](#). Intraoperative transfusions will be administered at the discretion of the investigator in accordance with standard institutional practice.

9.1.3. Postoperative phase through 30-day evaluation

Subjects will undergo scheduled study procedures as indicated in the Schedule of Assessments in [Appendix 4](#) until the point of discharge from index hospitalization. A Follow-up Evaluation will be performed 30 days after the index operation for vital status/mortality check. This can be done via telephone contact, in-person follow-up visit, or review of medical records.

Postoperative Antithrombotic Management:

Approaches to antiplatelet and anticoagulation management during the study are listed below and summarized in [Table 5](#). All subjects on preoperative aspirin should be maintained on the same therapy through-out the study. Additionally:

1. Any ACS subjects or those with recent coronary stent placement who *cannot* discontinue DAPT (i.e., clopidogrel, ticagrelor, etc.) for the recommended *preoperative washout* period will be excluded from study participation. Initiation of DAPT in the *postoperative* period is at the discretion of the investigator, or per their institutional protocols.
2. Timing of resumption for DOAC therapy in the postoperative period will be at the discretion of the investigator, based on the indication for anticoagulation and the anticipated bleeding risk.

Postoperative anticoagulation for venous thromboprophylaxis in all subjects should be administered according to standardized institutional protocols.

9.2. Safety and Tolerability Assessments

9.2.1. Adverse Events

Throughout the study, the Investigator or designee will determine adverse event (AE) occurrences. AE definitions, assignment of severity/seriousness/causality, and procedures for reporting SAEs, SADEs, and UADEs are detailed in [Appendix 1](#).

The condition of each subject will be monitored from the time of signing the Informed Consent Form (*assent* if signed by the legally authorized representative, or *consent* if signed by the individual) to the postoperative day 30 assessment. Subjects will be observed for any signs or symptoms and if possible, asked about their condition by open questioning, such as “How have you been feeling since you were last asked?”, at least once each day while in hospital and at each investigation visit. Subjects will also be encouraged to spontaneously report AEs occurring at any other time during the investigation.

If an AE occurs, appropriate diagnostic and therapeutic measures are to be taken and the investigation treatment may be discontinued if deemed clinically necessary. Follow-up evaluations of the subject are to be performed until the subject recovers or until the clinical Investigator considers the situation to be no longer clinically significant.

Adverse events are monitored and recorded on the AE form of the eCRF. In absence of a specific diagnosis, an individual AE form must be filled in for each sign or symptom. Changes from baseline laboratory values which are abnormal values and that are classified as clinically significant by the investigator (e.g., requiring medical intervention) must be recorded as AEs.

Persistent AEs will be entered once in the eCRF until they are resolved; a new event must be documented if deterioration occurs. These AEs will be carefully monitored. If an AE is still not resolved at the end of the investigation, this will be documented as “ongoing.” For recurrent AEs (i.e., AEs of the same nature, but with a different date of onset), an individual AE form must be completed for each of them.

Bleeding event AEs

All bleeding events are to be recorded as AE/SAEs by the Investigator or designee. Volume of blood loss and necessary transfusions will be documented in the corresponding eCRFs where applicable. In some cases, these events may contribute to the subject’s UDPB class. [35] Classifications are based on criteria/events occurring within the first postoperative day (as presented in [Table 1](#)) and will be determined based on the relevant data entered within the eCRFs.

Of note, UDPB counts transfusions of PRBCs, platelets, FFP, and Cryoppt beginning at chest closure. While intra-operative transfusions of these blood products prior to chest closure will be documented, they will not be counted as part of the UDPB classification or contribute to the primary endpoint. Preoperative transfusions are not counted in the UDPB classification. Transfusions of PCC and rFVIIa are counted beginning at the start of the procedure for UDPB. [35] Measurement of CTD volume begins at chest closure for UDPB classification. All subjects with events meeting criteria for UDPB classification of moderate, severe, or massive bleeding (Classes 2, 3 or 4) will be referred to the CEC for adjudication of UDPB bleeding class. Bleeding events occurring beyond the first postoperative day (i.e., not eligible for UDPB classification) will be adjudicated by the CEC for clinical severity. Details on the process for adjudication and relevant definitions are provided in the CEC Charter.

Postoperative Ischemic Events:

Postoperative ischemic events occurring during the index hospitalization will be captured as safety

endpoints in this study. This is with the intent of evaluating any potential risk for ischemic rebound in the setting of rapid antithrombotic drug removal. Postoperative ischemic events include myocardial infarction (MI), stroke, and urgent coronary revascularization. Of note, given the occasional complexities of distinguishing ischemic from hemorrhagic stroke (i.e., ischemic with hemorrhagic conversion), *all* postoperative strokes occurring during the index hospitalization will be captured within the safety endpoint.

All reported safety events occurring within 30 days of the study procedure that meet programmed criteria for cardiac ischemia or stroke will be submitted to the CEC for endpoint adjudication. All coronary revascularization procedures (regardless of open or percutaneous) that occur post-index procedure and during the follow-up period will be adjudicated by the CEC for the potential safety endpoint of *urgent coronary revascularization*. Details on endpoint definitions, adjudication criteria, and all other CEC processes/procedures are detailed in the CEC charter.

Venous Thromboembolic Events:

Postoperative venous thromboembolic events (VTEs) occurring during the index hospitalization will also be captured as safety endpoints in this study. These include clinically significant deep vein thromboses and pulmonary embolism. The intent is to identify any potential risk for thrombotic rebound in the setting of rapid anticoagulant removal.

All reported safety events occurring within 30 days of the study procedure that meet programmed criteria for VTE will be submitted to the CEC for endpoint adjudication. In addition to confirmation of VTE, the events will be evaluated by the CEC for clinical significance. Details on endpoint definitions, adjudication criteria, and all other CEC processes/procedures are detailed in the CEC charter.

Postoperative Mortality or AEs Resulting in Death

All deaths (including AEs resulting in death) that occur within 30 days of the study procedure will be adjudicated by the CEC for endpoint criteria. This includes assessment of the timing and nature of the mortality (cardiac vs. non-cardiac death). *For the purposes of this study, fatal bleeding will be considered a type of cardiac death.* Details on endpoint definitions, adjudication criteria, and all other CEC processes/procedures are detailed in the CEC charter.

Safety Reporting to the FDA

The Sponsor will provide safety reports (of adverse events, including relatedness to the device, severity, outcome/resolution, and all deaths) to the FDA for each set of 20 subjects enrolled. These reports are independent of the required annual reports for all IDEs.

The Sponsor will perform ongoing safety evaluations of any deaths as they occur in the study and share the information with the agency as requested. Specifically, if four or more of the 20 study subjects within each reporting set die within 72 hours of the device therapy, the Sponsor will send an immediate report of those deaths to the FDA for review.

9.2.2. Medical History

Medical history will be obtained at Screening and should include demographic information (date of birth, biologic sex, race, ethnicity) and subject's medical and surgical history. The medical history must be documented in the subject's eCRF.

9.2.3. Clinical Laboratory Evaluations

Blood samples will be collected and documented by the Investigator (or designee) for all clinical laboratory evaluations at the times indicated in the Schedule of Assessments in [Appendix 4](#). Local clinical laboratory assessments (including clinical chemistry, hematology, and coagulation tests) are listed in [Appendix 2](#). The handling and management of these samples will be per institutional protocols. **Of note:** if multiple sets of labs are obtained for a subject within the same post-operative day (either as part of standard institutional protocols, or due to changes in the subject's clinical picture), the lab assessments obtained at the time which *most closely approximates* those listed in **Table 6: Schedule of Assessments** should be the values entered into the EDC for study purposes.

Instructions for the collection and storage of study samples that will be analyzed by the Central Laboratory are provided in the Study Laboratory Manual.

9.2.4. Vital Signs

Supine blood pressure, pulse rate, respiratory rate, oxygen saturation, and body temperature will be assessed at the times indicated in the Schedule of Assessments in [Appendix 4](#). Vital signs may also be performed at other times if judged to be clinically appropriate, or if the ongoing review of the data suggests a more detailed assessment of vital signs is required.

All measurements will be performed singly and repeated once if outside the relevant clinical reference range.

9.2.5. Physical Examination

Body mass index will be calculated using the subject's body weight and height at the time of screening and documented with other demographic information (Schedule of Assessments, [Appendix 4](#)). A physical exam will be performed and documented at the time of screening/subject enrollment. Physical exams performed as part of standard of care on the day of screening but occurring prior to signing of informed consent may be documented as the screening PE. A physical exam will be repeated on the day of the procedure if the day of the procedure is different than the day of screening.

9.2.6. Other Assessments: Blood Products and Blood Loss

Intraoperative and postoperative blood loss and chest drainage volumes (chest drainage includes output from all chest and mediastinal tubes) will be measured and documented at the times indicated in the Schedule of Assessments in [Appendix 4](#). Cell Saver will **not** be included in the calculation of blood product transfusions, as this is volume that would normally be given back as part of standard of care. Chest tube drainage will be recorded in the corresponding *Chest Tube Drainage eCRF* for at least 24hrs post-operation, unless unable to do so (i.e., subject death prior to 24hrs). Volume of blood loss not coming from chest/mediastinal drainage will be documented separately, in the corresponding *Blood Loss (Non-Chest Drainage) eCRF* where applicable. Blood products received by the subject will be recorded in the corresponding *Transfusion eCRF*.

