 - Documentation of three unsuccessful attempts to contact the subject via telephone and/or by certified mail.

If a subject is withdrawn from treatment, the Sponsor will be notified and the date and reason(s) for the withdrawal will be documented in the subject's electronic Case Report Form (eCRF). For subjects who withdraw assent/consent and those withdrawn at the request of the Investigator, details of the reason for withdrawal will be captured to the extent possible. If a subject is withdrawn, efforts will be made to perform all follow-up assessments, if possible. Other procedures may be performed at the Investigator's (or designee's) and/or Sponsor's discretion. The Investigator (or designee) may also request that the subject return for an additional Follow-up Visit. All withdrawn subjects will be followed until resolution of all their AEs or until the unresolved AEs are judged by the Investigator (or designee) to have stabilized.

Subjects who are withdrawn for reasons not related to investigation treatment may be replaced following discussion between the Investigator and the Sponsor. For subjects who withdraw or discontinue at any point prior to completion of the required follow-up period, all available data will be used in the analysis, following the intent-to-treat principle. In cases where analysis criteria are not met, for example for the Per Protocol population, such subjects may not be included in the analysis. Subjects withdrawing or discontinuing early will be summarized as described in **Section 11.8**, and will be flagged in a listing of disposition information that includes reason for early withdrawal/discontinuation.

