9. STUDY ASSESSMENTS AND PROCEDURES

An outline of study assessments, procedures, labs, and associated time windows is given in the **Schedule of Assessments** ([Table 6](#) in [Appendix 4](#)). Subjects will be evaluated through the Follow-up evaluation at 30 days post-operation. Assessments and procedures that are recorded as Standard of Care (SOC) within the **Schedule of Assessments** are outside of the CIP and are optional. They may be recorded if they are performed in accordance with SOC at the particular institution. Failure to record an assessment/procedure that is listed as SOC will not be a violation of protocol. Required assessments and procedures (not denoted as SOC) that are not completed or that are completed outside of the specified windows will be recorded as a protocol deviation ([Section 13.2, 13.3](#)).

Reference [Section 4.3](#) for the full list of study endpoints. These endpoints require assessment of clinical events and/or treatments, blood product transfusions, drainage volume, and laboratory parameters. Definitions of analysis populations and description of statistical analyses of endpoints are briefly described in [Section 11](#) and will be detailed in the Statistical Analysis Plan (SAP) for the study.

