11.3. Effectiveness Analysis

The primary effectiveness endpoint will be evaluated using the Win Ratio method of analysis for a

hierarchical composite endpoint based on the Finkelstein-Schoenfeld test (Finkelstein and Schoenfeld, 1999; Pocock, et al., 2012) with three components ranked in order of clinical importance: a) fatal bleeding events occurring within 48hrs post-index procedure, b) moderate, severe, or massive perioperative bleeding events according to the Universal Definition of Perioperative Bleeding in Cardiac Surgery (UDPB) classification ≥ 2 , and c) 24-hour chest tube drainage (mL) following surgery. [14] [15] The Win Ratio assigns “wins”, “losses”, or “ties” in sequential comparisons between treatment and control arm subjects according to the hierarchical order of the components of the primary composite endpoint.

There are two key advantages to the Win Ratio method of analysis. First, the hierarchical assessment of the individual components of the composite endpoint according to their clinical significance. Second, the opportunity for different types of components, such as categorical versus continuous, to all be included thereby capturing all available information from each component to increase statistical power.[15] A Win Ratio along with a two-sided 95% CI will be estimated, and a Win Ratio greater than 1.0 favors the treatment arm; when the lower bound of a two-sided 95% confidence interval (CI) around the ratio exceeds 1.0, the treatment is shown to be statistically superior to control at alpha = 0.05.[16] The primary effectiveness analysis will use a combined DOAC population to evaluate the difference between the SOC (control) arm and the DrugSorb-ATR (investigational) arm. The key secondary effectiveness endpoints are drug removal endpoints, namely the percent change in pre-CPB vs. post-CPB apixaban and rivaroxaban levels as measured by liquid chromatography/tandem mass spectrometry (LC/MS-MS). Blood samples for drug removal analyses will be collected and analyzed by a central core laboratory.

Change from baseline in blood concentration of apixaban or rivaroxaban is defined as:

$$\frac{\text{pre-CPB [apixaban]blood} - \text{post-CPB [apixaban]blood}}{\text{pre-CPB [apixaban]blood}} * 100\%$$

and

$$\frac{\text{pre-CPB [rivaroxaban]blood} - \text{post-CPB [rivaroxaban]blood}}{\text{pre-CPB [rivaroxaban]blood}} * 100\%$$

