Benchtop studies of drug removal by DrugSorb-ATR (data on file, CytoSorbents Corporation) demonstrate concentration and time dependent absolute drug removal, which are nearly identical for both apixaban and rivaroxaban. Based on these benchtop studies, a conservative estimate of 40% reduction in blood concentration of DOAC between pre- and post- DrugSorb-ATR removal is expected, with a standard deviation of 40%, in the treatment arm. Minimal change is expected in the control arm. A two-sample t-test will be used to evaluate the difference between treatment arms. Due to highly variable baseline drug levels in the study population, percent change from baseline will be analyzed as opposed to observed values.

Additional secondary endpoints include 24-hour CTD (volume [mL]), total platelet transfusions during the index hospitalization (volume [mL] and units), and total PRBC transfusions during the index hospitalization (volume [mL] and units). Twenty-four-hour CTD (mL) will be assessed via two-sample t-test for mean difference. In the event the assumptions for a two-sample t-test are not met, a nonparametric test such as a Mann-Whitney test will be employed, with median and range values provided in the output. An additional analysis of 24-hour CTD will compare the frequency of subjects falling into volume categories (i.e., <500 mL, 500 to <750 mL, 750 to <1000 mL, 1000 to <1250 mL, 1250 to <1500 mL, and ≥ 1500 mL), and will use a Fisher-Freeman-Halton exact test to compare treatment groups. The transfusion endpoints will all be analyzed using two-sample t-tests for mean differences, and Fisher-Freeman-Halton exact tests for units. In the event the assumptions for a two-sample t-test are not met, a nonparametric test such as a Mann-Whitney test will be employed, with

median and range values provided in the output. The remaining Win Ratio component parts will also be included as secondary endpoints: proportions of fatal perioperative bleeding events will be assessed via Fisher's exact test; and proportions of UDPB events (by category) will be assessed via a Fisher-Freeman-Halton exact test. All surgical re-exploration for excessive bleeding, including those events occurring beyond the timeframe captured within the UDPB component of the primary endpoint will be captured as a secondary endpoint. Time to re-exploration will be considered.

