11.7. Treatment of Missing Data

Every effort will be taken to obtain data entry compliance of all critical fields during the study. The study assumes 5% of the primary effectiveness and safety data will be missing. Reasons for missing data will be collected and a distribution of the prognostic factors in subjects with and without missing data will be compared to identify any confounding factors. Sensitivity analyses will be conducted to assess the sensitivity of the results to assumptions underlying the missingness mechanism. Details will be provided in the SAP.

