^f In all females of childbearing potential. Performed in serum. Pre-consent test results done during the current admission MAY be used. Pre-consent test results done before the current admission MAY NOT be used.

^g Refer to [Appendix 2](#) for a list of evaluations in the hematology, clinical chemistry, cardiac biomarker, and coagulation tests. During Screening, if consented subjects enter the Operation Phase without post-consent evaluation of hematology, clinical chemistry, or coagulation tests to record, the last pre-consent laboratory values MAY be used. Intraoperative ACT is documented in the ACT log, and not recorded in the Coagulation Test eCRF.

^h Vital signs include supine blood pressure, pulse rate, respiratory rate, oxygen saturation, and body temperature.

ⁱ Duration of CPB = time from the start of CPB to end of CPB, which may differ from duration of operation. Flow rate and flow duration for the device will be recorded q30±5min while patient is on CPB; flow rates are not mandated while subject is on hypothermic circulatory arrest (HCA).

^j Details regarding the surgical type will be recorded. Delayed sternal closure will be recorded. *Re-exploration/re-thoracotomy will be recorded according to the same schedule as AEs and documented in the re-operation eCRF.*

^k ACT will be obtained once at 30min into CPB ±15min, and once within 30min post-protamine administration (post-CPB)

^l During the operation phase, arterial blood gas analysis will be obtained at the following time periods: within 30min pre-CPB, 30±15min into CPB, within 30min post-CPB, and upon admission to the ICU

- ^m Blood product administration will be monitored and recorded from the point of consent through discharge. Cell Saver will **not** be included as blood product administration. Blood loss and bleeding events will be monitored and recorded through follow-up, and drainage will be monitored from chest closure to 12h post-op (for UDPB class) and continued from 12hr post-op through at least 24h post-operation. Measurement of drainage after 24h and through time of chest/mediastinal drain removal will be per SOC.

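### Does the plan need a rule for 24-hour chest tube drainage cut short by a non-bleeding death?

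*Combined protocol and SAP*

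**What the plan says.** The primary endpoint (Sections 4.3.1 and 11.3) ranks fatal bleeding within 48 hours first, UDPB class 2 or higher second, and "24-hour chest tube drainage (mL) following surgery" third. The same volume is the first secondary endpoint after the two drug-removal endpoints: "Twenty-four-hour CTD (mL) will be assessed via two-sample t-test for mean difference".

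Section 9.2.6 asks for drainage to be recorded "for at least 24hrs post-operation, unless unable to do so (i.e., subject death prior to 24hrs". This governs recording and says nothing about analysis.

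Three other places come near the question:

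- Section 4.4.4 says of subjects who withdraw or discontinue that "all available data will be used in the analysis, following the intent-to-treat principle". It does not name death.
- Section 9 says that the endpoint analyses "will be detailed in the Statistical Analysis Plan (SAP) for the study".
- Section 11.7 assumes 5% missing primary data and says "Sensitivity analyses will be conducted to assess the sensitivity of the results to assumptions underlying the missingness mechanism", again leaving detail to the SAP.

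Two passages bear on how an early death is classed on the second component. Section 9.2.1 states "Transfusions of PCC and rFVIIa are counted beginning at the start of the procedure for UDPB", while the other blood products count from chest closure. Table 6, footnote m, states "drainage will be monitored from chest closure to 12h post-op (for UDPB class".

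**The concern.** A subject who dies of a non-bleeding cause before 24 hours is not separated on the first component. If the subject is also tied with a comparator on UDPB, the pair is settled on drainage. A volume collected over a few hours is smaller than one collected over 24, so the death would usually be scored as a win. That is the wrong direction for an endpoint ranked by clinical importance. It could push the test towards the arm with more early deaths, and the secondary t-test would inherit the same distortion. If the scoring choice were left until unblinded results existed, it could also be made with the answer in view.

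**Working it through.** **Inputs from the plan.** Section 11.1 and Table 3 (apixaban equal to rivaroxaban) give fatal bleeding 3% in both arms, UDPB class 2 or higher 24.3% against 40.5%, drainage 480 against 800 mL with SD 253, and 57 evaluable per arm (Table 3 uses 56). Section 11.6 gives a final boundary of Z = 2.00, a one-sided level of 2.28%.

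**Assumed, because the documents are silent.** The rate and timing of non-bleeding deaths before 24 hours (uniform in time), and the drainage pattern: either uniform over 24 hours or front-loaded with a 6-hour constant.

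**The plan's own figure.** Simulating the Finkelstein-Schoenfeld test on these inputs gives power of 99.5% at 56 per arm (Table 3: 99.5%) and 91.9% at the interim with 39 per arm (Table 3: 91.3%). The model therefore matches the plan.

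**One early death, no bleeding effect in either arm.** Take a subject without fatal bleeding or UDPB class 2 or higher.

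- Pairs won before drainage is reached: 0.03 + 0.97 × 0.405 = 0.423. The other 0.577 reach drainage.
- Let f be the share of the 24-hour volume collected by death. The chance of winning such a pair is Φ[800(1 − f) / (253√(1 + f²))].
- Death at hour 6: f = 0.25 (uniform) gives Φ(2.30) = 99%; f = 0.64 (front-loaded) gives Φ(0.95) = 83%.
- Hour 12 gives 61 to 92%, and hour 18 gives 53 to 74%.
- Shift in the overall win proportion for an hour-6 death: 0.577 × (0.83 − 0.50)/57 = 0.003, up to 0.577 × (0.99 − 0.50)/57 = 0.005.
- The ranking has almost no ties, so the null standard error of the win proportion is √[115/(12 × 57 × 57)] = 0.054. One such death moves Z by about 0.06 to 0.09.

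**Whole trial.** False device wins at Z > 2.00 with no bleeding effect, 57 per arm, 10,000 trials per scenario (Monte Carlo error about 0.15 points). At 57 per arm, 5%, 10% and 15% are about 3, 6 and 9 subjects.

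| Early non-bleeding deaths, device vs control | Partial volume taken at face value |
|---|---|
| none | 2.3% |
| 5% vs 5% | 2.3% |
| 5% vs 3% | 2.6–2.8% |
| 10% vs 5% | 2.8–3.6% |
| 15% vs 5% | 3.7–5.7% |
| 5% vs 10% | 1.3–1.8% |

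Scoring a tie on drainage gives 2.0 to 2.9% in every scenario. A second simulation at 56 per arm, with an extreme 10% against 0%, gives 4.2% for partial volume, 2.3% for a tie and 2.1% for exclusion.

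**How far the inflation depends on the UDPB model.** The table gives early deaths the ordinary UDPB risk, reduced when death comes first. Subjects who die within a day of urgent cardiac surgery may well have met class 2 already, through PCC or rFVIIa, delayed closure, transfusion or re-exploration; they then lose on the second component to anyone who has not. In a further run of 6,000 trials at 10% against 5% (Monte Carlo error about 0.2 points), the face-value figure was 3.2 to 3.5% under the table's model, 2.3 to 2.7% if 60% of early deaths carry class 2 or higher, and 2.0 to 2.3% if 80% do. Both percentages are assumptions.

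**Power under the design effect.** With equal early deaths of 3 to 10% per arm, power is 96.9% or higher whether the volume is taken at face value, ranked worst, tied or excluded.

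**Secondary t-test.** One control-level death at hour 6 shifts the mean difference by 800(1 − f)/57 = 5 to 11 mL, against a standard error of 253√(2/57) = 47 mL. Taken alone, false device wins are 2.4 to 2.6% at 5% vs 5% and 3.8 to 5.6% at 10% vs 5%. The endpoint is tested only after the primary and both drug-removal endpoints succeed.

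**The case for a change.** The best case for acting is that the plausible rules do not agree. With deaths of 10% against 5% under the design effect, the median win ratio runs from 2.15 (any early death placed in the top tier) to 2.84 (partial volume), and power from 91.5% to 99.6%. Section 4.4.4, read literally, points to the partial volume, which is the one reading that rewards an early death. An unblinded interim is planned, and writing a rule costs little.

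Part of this stands. No rule is stated in the protocol text, and the choice belongs in the SAP before unblinded data are seen. The rest is weaker:

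- The spread comes mostly from the options that penalise the death. Placing it in the top tier redefines the primary endpoint, although Section 3 explains why only bleeding deaths count. Ranking it worst on drainage scores a non-bleeding death as the heaviest bleeding.
- Between the two rules that leave the endpoint as defined, the difference is slight: a median win ratio of 2.77 to 2.78 for a tie against 2.79 to 2.84 for partial volume, with power of 99.0% or higher for both.
- Section 4.4.4 concerns withdrawal and discontinuation. A 24-hour value never observed because of death fits more naturally under Section 11.7.

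One apparent safeguard should not be relied on. The report in Section 9.2.1 for four or more deaths in a set of 20 counts deaths per set, not per arm, so it does not reveal an imbalance. The arm comparison would come from the mortality endpoints in Section 4.3.6.

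**Conclusion.** No change to the plan follows. This is a missing detail, and no stated rule is shown to be wrong. The protocol says where such detail belongs, and the SAP may already hold it. An analyst meeting a six-hour volume would see that it is not a 24-hour one, and treating it as missing or tied keeps the error rate close to nominal in every scenario tried.

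Even the least favourable reading does little harm: 2.3% false device wins at equal early-death rates, and 2.8 to 3.6% at 10% against 5%. It takes an assumed 15% against 5% to reach 3.7 to 5.7%. The distortion reverses when the excess is in the control arm.

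These figures rest on assumed death rates, uniform death times, two drainage patterns and an assumed UDPB risk among early deaths. A higher UDPB risk in those subjects brings the 10% against 5% figure down to 2.0 to 2.7%. The conclusion would weaken only if early non-bleeding deaths without UDPB class 2 or higher were both common and strongly unequal between arms, and nothing in the documents suggests that.
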